Appendix III. Frequently asked questions

Question	Answer
What should be done if several unique lesions at baseline become confluent at a follow up evaluation?	Measure the longest diameter of the confluent mass and record to add into the sum of the longest diameters
How large does a new lesion have to be to count as progression? Does any small subcentimetre lesion qualify, or should the lesion be at least measurable?	New lesions do not need to meet 'measurability criteria' to be considered valid. If it is clear on previous images (with the same technique) that a lesion was absent then its definitive appearance implies progression. If there is any doubt (because of the techniques or conditions) then it is suggested that treatment continue until next scheduled assessment when, generally, all should be clear. Either it gets bigger and the date of progression is the date of the first suspicion, or it disappears and one may then consider it an artefact with the support of the radiologists
How should one lesion be measured if on subsequent exams it is split into two?	Measure the longest diameter of each lesion and add this into the sum
Does the definition of progression depend on the status of all target lesions or only one?	As per the RECIST 1.1 guideline, progression requires a 20% increase in the sum of diameters of all target lesions AND a minimum absolute increase of 5 mm in the sum
Are RECIST criteria accepted by regulatory agencies?	Many cooperative groups and members of pharma were involved in preparing RECIST 1.0 and have adopted them. The FDA was consulted in their development and supports their use, though they don't require it. The European and Canadian regulatory authorities also participated and the RECIST criteria are now integrated in the European note for guidance for the development of anticancer agents. Many pharmaceutical companies are also using them. RECIST 1.1 was similarly widely distributed before publication
What is the criterion for a measurable lesion if the CT slice thickness is >5 mm?	RECIST 1.1 recommends that CT scans have a maximum slice thickness of 5 mm and the minimum size for a measurable lesion is twice that: 10 mm (even if slice thickness is <5 mm). If scanners with slice thickness >5 mm are used, the minimum lesion size must have a longest diameter twice the actual slice thickness
What should we record when target lesions become so small they are below the 10 mm 'measurable' size?	Target lesion measurability is defined at baseline. Thereafter, actual measurements, even if <10 mm, should be recorded. If lesions become very small, some radiologists indicate they are 'too small to measure'. This guideline advises that when this occurs, if the lesion is actually still present, a default measurement of 5 mm should be applied. If in fact the radiologist believes the lesion has gone, a default measurement of 0 mm should be recorded
If a patient has several lesions which have decreased in size to meet PR criteria and one has actually disappeared, does that patient have PD if the 'disappeared' lesion reappears?	Unless the sum meets the PD criteria, the reappearance of a lesion in the setting of PR (or SD) is not PD. The lesion should simply be added into the sum. If the patients had had a CR, clearly reappearance of an absent lesion would qualify for PD
When measuring the longest diameter of target lesions in response to treatment, is the same axis that was used initially used subsequently, even if there is a shape change to the lesion that may have produced a new longest diameter?	The longest diameter of the lesion should always be measured even if the actual axis is different from the one used to measure the lesion initially (or at different time point during follow up) The only exception to this is lymph nodes: as per RECIST 1.1 the short axis should always be followed and as in the case of target lesions, the vector of the short axis may change on follow up
Target lesions have been selected at baseline and followed but then one of these target lesions then becomes non evaluable (i.e. different technique used) What is the effect this has on the other target lesions and the overall response?	What may be done in such cases is one of the following: (a) If the patient is still being treated, call the centre to be sure that future evaluations are done with the baseline technique so at least SOME courses are fully evaluable (b) If that is not possible, check if there IS a baseline exam by the same technique which was used to follow patients...in which case if you retrieve the baseline measures from that technique you retrieve the lesion evaluability (c) If neither (a) nor (b) is possible then it is a judgement call about whether you delete the lesion from all forms or consider the impact of the lesion overall is so important that its being non evaluable makes the overall response interpretation inevaluable without it. Such a decision should be discussed in a review panel It is NOT recommended that the lesion be included in baseline sums and then excluded from follow up sums since this biases in favour of a response

(continued on next page)

Appendix III continued

Question	Answer
What if a single non target lesion cannot be reviewed, for whatever reason; does this negate the overall assessment?	Sometimes the major contribution of a single non target lesion may be in the setting of CR having otherwise been achieved: failure to examine one non target in that setting will leave you unable to claim CR. It is also possible that the non target lesion has undergone such substantial progression that it would override the target disease and render patient PD. However, this is very unlikely, especially if the rest of the measurable disease is stable or responding
A patient has a 32% decrease in sum cycle 2, a 28% decrease cycle 4 and a 33% decrease cycle 6. Does confirmation of PR have to take place in sequential scans or is a case like this confirmed PR?	It is not infrequent that tumour shrinkage hovers around the 30% mark. In this case, most would consider PR to have been confirmed looking at this overall case. Had there been two or three non PR observations between the two time point PR responses, the most conservative approach would be to consider this case SD
In the setting of a breast cancer neoadjuvant study, would mammography not be used to assess lesions? Is CT preferred in this setting?	Neither CT nor mammography are optimal in this setting. MRI is the preferred modality to follow breast lesions in a neoadjuvant setting
A patient has a lesion measurable by clinical exam and by CT scan. Which should be followed?	CT scan. Always follow by imaging if that option exists since it can be reviewed and verified
A lesion which was solid at baseline has become necrotic in the centre. How should this be measured?	The longest diameter of the entire lesion should be followed. Eventually, necrotic lesions which are responding to treatment decrease in size. In reporting the results of trials, you may wish to report on this phenomenon if it is seen frequently since some agents (e.g. angiogenesis inhibitors) may produce this effect

Appendix 4. Criteria for Progression in Castration-Resistant Prostate Cancer

Variable	Criteria
PSA	
Ignore early rises (prior to 12 weeks) in determining PSA response For control/relieve/eliminate endpoints: Percent change from baseline at 12 weeks and maximal change at any time using a waterfall plot. Progression: Decline from baseline: record start of therapy to first PSA increase that is $\geq 25\%$ and ≥ 2 ng/mL above the nadir and confirmed by a second value 3 or more weeks later. No decline from baseline: PSA progression $\geq 25\%$ and ≥ 2 ng/mL after 12 weeks

Soft tissue	
Use RECIST with caveats: Only report changes in lymph nodes that were ≥ 2 cm in diameter at baseline Record changes in nodal and visceral soft tissue sites separately Record complete elimination of disease at any site separately Confirm favorable change with second scan

Bone	
The appearance of ≥ 2 new lesions, and, for the first reassessment only, a confirmatory scan performed 6 or more weeks later that shows a minimum of 2 or more additional new lesions The date of progression is the date of the first scan that shows the change

Appendix 5. Lymphoma Efficacy Assessments

Tumor Status Assessments

The determination of lymphoma response and progression will be based on standardized criteria {Cheson et al 2007, Owen et al 2013} as specifically modified for this study to reflect the biology of the diseases under study. During the course of the study, investigators will periodically assess the status of each subject's lymphoma.

Method of Assessment

In addition to clinical examination, imaging-based evaluation will be used in this study in all subjects enrolled. CT scan is the preferred method for radiographic tumor assessment. MRI scanning may be used at the investigator's discretion in subjects for whom this may be a preferred alternative to CT scanning; however, if MRI is performed, a non-contrast CT of the chest should also be performed. Contrast-enhanced scanning is preferred, but iodine-containing or gadolinium contrast material may be omitted in subjects for whom use of a contrast agent would be medically contraindicated. If available, positron emission tomography (PET) scan data will be considered in response and progression assessment; however, PET scanning will not be a required component of assessment in this study. As appropriate, bone marrow aspirate/biopsy information (eg, for confirmation of CR) will be also be considered. Clinical palpation, chest x-ray, ultrasound, endoscopy, laparoscopy, radionuclide scan, or tumor markers will not be considered for response assessment.

For radiographic assessments, the same method of assessment and the same technique (eg, scan type, scanner, subject position, dose of contrast, injection/scan interval) should be used to characterize each identified and reported lesion at baseline, while on study drug treatment and during follow-up. Furthermore, the use of IV contrast should be consistent across time points. In the event that the screening/baseline CT scan of the neck, chest, abdomen, and pelvis is performed without IV contrast, follow-up time points should also be performed without IV contrast.

All relevant radiographic and clinical information required to make each tumor status assessment must be made available for source verification and for submission to the IRC.

Timing of Assessments

During screening, clinical and imaging-based tumor assessments should be performed within the specified screening period. On-study CT/MRI tumor assessments should be performed as indicated in Section 6.1.10. An end-of-study CT/MRI tumor assessment should be performed unless the subject already has radiographic confirmation of disease progression ≤ 4 weeks prior to study discontinuation. If a subject permanently discontinues study drug prior to objective documentation of lymphoma progression, investigators should continue further follow-up at ~8-week intervals until lymphoma progression is documented.

Identification and Follow-up of Tumor Lesions and Organomegaly

Index Lesions

Up to 6 lesions (eg, lymph nodes, liver or spleen nodules, and/or other circumscribed extra-nodal masses) should be selected as index lesions that will be used to quantitate the status of the disease during study. Ideally, the index lesions should be located in disparate regions of the body and include mediastinal, abdominal, and retroperitoneal areas of disease whenever these sites are involved.

Index lesions will be measured and recorded at baseline and at the stipulated intervals. The cross-sectional dimensions (the largest cross-sectional diameter, ie, the longest diameter [LD] × the longest perpendicular diameter [LPD]) will be recorded (in cm) for each index lesion. Using the LD and LPD, the product of the perpendicular diameters (PPD) for each index lesion will be calculated. The sum of the products (SPDs) for all index lesions will be calculated and recorded. The baseline SPDs will be used as references by which objective tumor response will be characterized during treatment. The nadir LDs of individual lesions and the nadir SPDs will be used as references by which objective tumor progression will be characterized during study. All PPD and SPD measurements will be reported in centimeters squared.

Nodal Index Lesions

A nodal mass may be selected as a nodal index lesion if it is both abnormal and measurable at baseline. A lymph node lesion is considered abnormal if it has a single diameter that is >1.0 cm and is considered measurable if it has 2 perpendicular diameters that can be accurately measured in cross section with the LD being ≥ 1.0 cm and the LPD also being ≥ 1.0 cm.

Abnormal, measurable nodal lesions will be subcategorized as either large or small.

- Large nodal lesions have an LD that is >1.5 cm and an LPD that is ≥ 1.0 cm.
- Small nodal lesions have an LD that is >1.0 cm and ≤ 1.5 cm and an LPD that is >1.0 cm.

Index lesions measuring >1.5 cm in the LD, regardless of the measurement of the LPD, will be prioritized during baseline index lesion selection.

At follow-up time points, the SPD of all nodal index lesions will be considered. Because nodal index lesions that have one or both diameters >0 cm and <1.0 cm cannot be reliably measured, a default value of 1.0 cm will be assigned for each diameter that meets these criteria and the resulting PPD will be used in SPD calculations. Based on this convention, a CR may be achieved even if an SPD value is >0 cm² (ie, if all lymph nodes measure ≤ 1.0 cm²).

New or enlarging nodal lesions that are still ≤ 1.0 cm by ≤ 1.0 cm will not be considered to represent recurrent disease or PD. A new node that measures >1.5 cm in any diameter or a new node that measures >1.0 cm to ≤ 1.5 cm in the LD and measures >1.0 cm in the LPD will be considered PD.

In cases in which a large lymph node mass has split into multiple components, only those elements that are >1.0 cm in at least 1 diameter will be considered abnormal and used in calculating the SPD. Components that are ≤ 1.0 cm in the LD are assumed to be normal lymph node structures. PD will not be based on the growth of a lesion sub-component until it meets the criteria for abnormal. Lesion sub-components that are abnormal (>1.0 cm in ≥ 1 diameter) will have the true PPDs calculated with the result used only for calculating an accurate nadir. Lesion sub-components that are normal (≤ 1.0 cm in the LD) will have the default PPD of 1.0 cm^2 ($1.0 \text{ cm} \times 1.0 \text{ cm}$) stored only for the purposes of calculating the nadir value.

If lesions merge, a boundary between the lesions will be established so the LD of each individual lesion can continue to be measured. If the lesions have merged in a way that they can no longer be separated by this boundary, the newly merged lesion will be measured bi-dimensionally.

Extra-Nodal Index Lesions

An extra-nodal mass may be selected as an index lesion if it is both abnormal and measurable at baseline. An extra-nodal mass of any size is considered abnormal. It is considered measurable at baseline if it has 2 perpendicular diameters that can be accurately measured in cross section with the LD being ≥ 1.0 cm and the LPD also being ≥ 1.0 cm.

At follow-up time points, the PPD of each single extra-nodal index lesion and the SPD of all extra-nodal index lesions will be considered. Because extra-nodal index lesions that have one or both diameters >0 cm and < 1.0 cm cannot be reliably measured, a default value of 1.0 cm will be assigned for each diameter that meets these criteria and the resulting PPD will be used in SPD calculations. If an extra-nodal lesion is no longer clearly visible, it will be considered resolved and its PPD will be defined as 0 cm^2 .

If an extra-nodal lesion that had resolved (ie, had a PPD of 0 cm^2) subsequently reappears unequivocally, the subject will be considered to have PD. A new unequivocal extra-nodal lesion of any size that appears at a site that was not previously involved with lymphoma and is discernible to the radiologist by CT scan will be considered PD.

Non-Index Lesions

Any other measurable and abnormal nodal or extra-nodal lesions not selected for quantitation as index lesions may be considered non-index lesions. In addition, non-measurable evidence of lymphoma such as abnormal, non-measurable nodal lesions, extra-nodal lesions with both diameters < 1.0 cm, bone lesions, leptomeningeal disease, ascites, pleural or pericardial effusions, lymphangitis of the skin or lung, abdominal masses that are not confirmed and followed by imaging techniques, cystic lesions, previously irradiated lesions, or lesions with artifacts may be considered as non-index disease.

If present at baseline, up to 6 non-index lesions should be recorded. Measurements are not required.

Non-index disease will be used as a general reference to further characterize regression or progression of lymphoma during assessments of the objective tumor response during treatment. These lesions should be followed as “present” or “absent”.

Spleen and Liver

Qualitative assessments of the sizes of the spleen and liver will be performed. In addition, the presence or absence of splenic and/or hepatic nodules will be recorded.

Bone Marrow

Bone marrow assessments will be based on morphologic evaluation of bone marrow biopsies. Immunohistochemistry may be used to assess response if the sample is indeterminate by morphology.

In a subject who has a baseline bone marrow biopsy showing bone marrow involvement with lymphoma or does not have a baseline bone marrow examination, declaration of an on-study CR requires bone marrow biopsy documentation of the absence of bone marrow lymphoma. In a subject who has a baseline bone marrow biopsy showing no evidence of lymphoma, declaration of an on-study CR does not require bone marrow examination as long as other criteria for CR are met.

Definitions of Tumor Response and Progression

Responses will be categorized as complete response (CR), partial response (PR), stable disease (SD), or progressive disease (PD). In addition, a response category of not evaluable (NE) is provided for situations in which there is inadequate information to otherwise categorize response status.

The best overall response will be determined. The best overall response is the best response recorded from the start of study drug until PD/recurrence (taking as reference for PD the smallest measurements recorded since study drug started). Subjects with a best overall response of NE will be included in the denominators in calculations of tumor response rate.

Response Categories

Complete Response

To satisfy criteria for CR, all of the following criteria must be met:

- No evidence of new disease
- Regression of all index nodal lesions to normal size (≤ 1.5 cm in the LD for nodes that were considered large at baseline and ≤ 1.0 cm in the LD and ≤ 1.0 cm in the LPD for nodes that were considered small at baseline) (see Nodal Index Lesions section for definitions of large and small nodes)
- Regression to normal of all nodal non-index disease

- Disappearance of all detectable extra-nodal index and non-index disease
- Normal spleen and liver size by imaging studies, no hepatic or splenic lymphoma nodules, and no new liver or spleen enlargement
- Morphologically negative bone marrow based on an adequate unilateral core biopsy if the sample is indeterminate by morphology, it should be negative by immunohistochemistry
- If PET performed (not required), no evidence of residual disease

Partial Response

To satisfy criteria for PR, all of the following criteria must be met as noted below:

- No evidence of new disease
- A $\geq 50\%$ decrease from baseline in the SPD of the index lesions
- No increase in the size of non-index disease
- No increase in the size of the liver or spleen and no new liver or spleen enlargement
- Persistence of bone marrow involvement in a subject who meets other criteria for CR based on the disappearance of all nodal and extra-nodal masses
- If PET performed (not required):
 - Typically FDG-avid lymphoma: if no baseline PET scan or if the PET scan was positive before initiating study drug(s), the on-treatment PET is positive in ≥ 1 previously involved site. If baseline PET was performed and was negative, there is no new PET evidence of disease
 - Variably FDG-avid lymphoma/FDG-avidity unknown: if no pretreatment PET scan or if the pretreatment PET scan was negative for lymphoma, CT criteria should be used in assessing the tumor during study. If the PET scan was positive before initiating study drug(s), the on-treatment PET is positive in ≥ 1 previously involved site.

Stable Disease

To satisfy criteria for SD, all of the following criteria must be met:

- No evidence of new disease
- Neither sufficient tumor shrinkage from baseline to qualify for PR nor sufficient evidence of tumor growth to qualify for PD

Progressive Disease

The occurrence of any of the following events indicates progressive disease (PD):

- Evidence of any new disease that was not present at baseline:
 - A new node that measures >1.5 cm in LD and > 1.0 cm in the LPD.
 - A new node that measures >1.0 cm to ≤ 1.5 cm in the LD and >1.0 cm in the LPD
 - Unequivocal reappearance of an extra-nodal lesion that had resolved (ie, had previously been assigned a PPD of 0 cm^2)
 - A new unequivocal extra-nodal lesion of any size
 - New non-index disease (eg, effusions, ascites, or other organ abnormalities) of any size unequivocally attributable to lymphoma (usually requires PET, biopsy, cytology, or other non-radiologic confirmation to confirm disease attributable to lymphoma).

Note: Isolated new effusions, ascites, or bone lesions are not sufficient evidence alone of PD unless histologically confirmed. In subjects with no prior history of pulmonary lymphoma, new lung nodules identified by CT are usually benign. Thus, a declaration of PD should not be made if this is the only manifestation of an apparently new lesion.
 - New or recurrent bone marrow involvement with lymphoma if the last prior bone marrow biopsy performed as part of the study (baseline or on-study) was negative for lymphoma
- Evidence of worsening of nodal or extra-nodal index lesions:
 - Increase from the nadir by $\geq 50\%$ in the SPD of index lesions
 - Increase from the nadir by $\geq 50\%$ in the LD of an individual node or extra-nodal mass that now has an LD of >1.5 cm and an LPD of > 1.0 cm
- Unequivocal increase in the size of non-index disease
- If PET performed (not required):
 - The appearance of any new lesion compatible with lymphoma with confirmation by other radiographic or histological modalities
 - The reappearance of any activity in a pre-existent lesion that meets size criteria for a new lesion on CT

Note: If there is uncertainty regarding whether there is definitive lymphoma progression, the subject should continue study drug and remain under close observation (eg, evaluated at scheduled intervals). In particular, worsening of constitutional symptoms in the absence of objective evidence of worsening lymphoma will not be considered definitive disease progression; in such subjects, both lymphoma -related and non-lymphoma -related causes for the constitutional symptoms should be considered. Transient worsening of disease during temporary interruption of study drug(s) (eg, for intercurrent illness) may also not indicate definitive disease progression. In these instances, CT/MRI should be attempted in order to document whether definitive disease progression has occurred. If subsequent evaluations suggest that the subject has experienced persistent definitive disease progression, then the date of progression will be the time point at which progression was first objectively documented.

Non-Evaluable

In a subject who does not have evidence of PD, the occurrence of any of the following conditions indicates a response status of NE:

- There are no images or inadequate or missing images.

Note: A time-point will be considered to have a response of NE if any index lesion is missing. PD may be assigned at any time point regardless of the extent of missing index or non-index lesions. Missing non-index lesions will not impact the ability to assess for response or disease progression.

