exam, vitals, ECG, collection of blood samples (for routine safety labs, GS-5829 PK, PD markers, and biomarkers at applicable visits), urine pregnancy test (every 4 weeks while receiving GS-5829 in female of childbearing potential), and assessment of AEs. In addition, subjects will undergo CT/MRI or applicable scans every 8 weeks for the first year and then every 12 weeks. Subjects in Group 3 will undergo a PET/CT if available instead of a CT scan alone at week 16. A subject who does not show evidence of disease progression by clinical assessment or by CT/MRI or applicable scan may continue receiving GS-5829 once daily until disease progression (clinical or radiographic), unacceptable toxicity, withdrawal of consent, or other reasons specified in Section 3.5.

Plasma samples for GS-5829 PK will be collected (\pm 10 minutes) in cohorts 1-3 of Group 1 on Study Day 1 at pre-dose (0hr), 0.5, 1, 2, 3, 4, 6, 8, 12, and 24 hours post-dose and in cohorts 4-8 of Group 1 and all cohorts of Group 2 on Cycle 1 Day 1 at pre-dose (0 hr), 0.5, 1, 2, 3, 4, 6, 8, 12, and 24 hours post-dose. Additional samples will be collected at 48 and 72 hours post-dose in cohorts 1 – 3 of Group 1 relative to first dose of GS-5829. Plasma samples for GS-5829 PK will be collected in all cohorts (Group 1 and Group 2) at pre-dose (0 hr), 0.5, 1, 2, 3, 4, 6, 8, 12, and 24 hours post-dose relative to GS-5829 administration on Cycle 1 Day 8. Sparse PK samples will be collected in all cohorts (Group 1 and Group 2) at trough (20-26 hours post-dose) on Cycle 1 Day 4, 2 - 4 hours post-dose on Cycle 1 Day 15, and anytime post-dose on Day 1 of Cycles 2 through 6. In one or more cohorts, PK samples will be collected on Day 1 of Cycle 2 at pre-dose and 0.5, 1, 2, 3, 4, 6, 8, and 24 hours post-dose. GS-5829 dose will be administered in fed state on Day 1 of Cycle 2.

Urine will be collected for GS-5829 PK in Group 1 cohorts 1-3 on Study Day 1 and in Group 1 cohorts 4-8 on Cycle 1 Day 1 at pre-dose, 0-6 hours, 6-12 hours, and 12-24 hours post-dose relative to first dose of GS-5829.

Subjects in the Group 3 lymphoma expansion will have PK drawn at pre-dose, 1, 2, 4, 6, and 24 hours post-dose on Cycle 1, Day 8. PK samples will also be drawn at pre-dose on Day 1 of Cycles 2, 4, and 6.

After discontinuation of treatment, subjects will be followed for safety for 30 days.

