6.1.12. PET/CT Scan

Subjects who are enrolled in Group 3 (DLBCL or PTCL) will undergo a positron emission tomography (PET) and CT scan at Screening and at Week 16 to evaluate response, unless the subject has demonstrated disease progression prior to this date.

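### Appendix 5 leaves a lymphoma subject with adequate CT shrinkage, a residual mass and a negative on-treatment PET in neither CR nor PR at that visit, which can understate the response rate when no other visit qualifies

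*Protocol*

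**What the plan says.** **CR (Protocol Appendix 5).** The list opens with "To satisfy criteria for CR, all of the following criteria must be met". One item is "Regression of all index nodal lesions to normal size", which for a node that was large at baseline means a longest diameter of at most 1.5 cm. Extra-nodal disease must have gone. The PET item, "If PET performed (not required), no evidence of residual disease", is a further condition; nothing lets a negative PET stand in for size.

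**PR (Appendix 5).** The list opens with "To satisfy criteria for PR, all of the following criteria must be met as noted below". It asks for an SPD at least 50% below baseline and adds PET conditions that apply if PET was done:
- Typically FDG-avid disease: "if no baseline PET scan or if the PET scan was positive before initiating study drug(s), the on-treatment PET is positive in" at least one previously involved site. If the baseline PET was negative, it is enough that PET shows nothing new.
- Variably avid disease, or avidity unknown: CT criteria apply if the pretreatment PET was absent or negative. If it was positive, the on-treatment PET must again be positive in at least one previously involved site.

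**Other categories (Appendix 5).** Stable disease (SD) is defined by "Neither sufficient tumor shrinkage from baseline to qualify for PR nor sufficient evidence of tumor growth to qualify for PD", with no new disease. Not evaluable (NE) is for absent, inadequate or missing images. Best overall response (BOR) is the best category reached between the start of study drug and progression or recurrence.

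**Timing.** Protocol Section 6.1.12 gives Group 3 a PET and CT "scan at Screening and at Week 16 to evaluate response". The Synopsis and Section 3.3 are conditional: "Subjects in Group 3 will undergo a PET/CT if available instead of a CT scan alone at week 16". Appendix 5 treats PET as optional but takes it into account where it exists. CT or MRI is every 8 weeks in the first year.

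**Use of response.** The primary endpoint is DLT incidence (Protocol 8.1.2). Protocol 8.5 only lists the overall response rate (ORR). SAP 6.1.2.2 calculates it with an exact 95% CI. SAP 6.1.1.2 bases lymphoma response on the Cheson criteria and does not mention that Appendix 5 modifies them for this study.

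**The concern.** The two lists do not meet. A residual mass blocks CR on size, and a negative PET blocks PR, so a subject who has shrunk well and is metabolically clear satisfies neither. The same subject without a PET would meet the PR shrinkage criterion. A more favourable scan produces a less favourable classification.

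The condition is also inconsistent within the PR list. A typically avid subject whose baseline PET was negative can be PR with no positive on-treatment PET, so PET positivity is not treated as essential to a partial response.

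Group 3 may add up to 34 subjects partly to look at efficacy, and the Week 16 PET is there to judge response. If the rule is applied as written, some genuine responses could be left out of ORR, and whether that happens would depend on whether a PET was done.

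**Working it through.** **1. The plan's own figure.** The maximum Group 3 size (Protocol Section 3.2, Table 3-3) is 6 + 34 = 40 at the first level, or 6 + 6 + 28 = 40 if the lower level is used. Both reproduce. The documents give no assumed response rate, power or response-based sample size.

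**2. A single case.** Baseline PET positive; one index node goes from 4 × 4 cm to 2 × 2 cm. SPD goes from 16 to 4 cm², a fall of 12/16 = 75%. The on-treatment PET is negative.
- CR: fails, because 2 cm exceeds 1.5 cm.
- PR: shrinkage is met (75% against 50%), but the PET condition fails.
- SD: does not fit literally, because the shrinkage is enough for PR.
- NE: does not fit, because the images exist and are adequate.

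**3. All PET-negative combinations.** Hold the CT fixed: SPD down at least 50%, residual mass above normal size, no new disease.

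| Avidity | Baseline PET | On-treatment PET negative | No on-treatment PET |
|---|---|---|---|
| Typical | Absent | Neither CR nor PR | PR |
| Typical | Negative | PR | PR |
| Typical | Positive | Neither CR nor PR | PR |
| Variable/unknown | Absent | PR | PR |
| Variable/unknown | Negative | PR | PR |
| Variable/unknown | Positive | Neither CR nor PR | PR |

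Three of the six PET-negative cells fall in the gap, including both with a positive baseline PET. With no on-treatment PET, none does.

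**4. From visit to BOR.** Take CT at Weeks 8, 16 and 24, a negative PET at Week 16 only, and no progression in between. Seven patterns have qualifying shrinkage at one or more visits. A qualifying CT at Week 8 or Week 24 gives PR at that visit, and BOR keeps it. Only one of the seven loses the response: shrinkage at Week 16 alone. The patterns are not equally likely, so 1/7 is not a probability.

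**5. Size.** Each subject lost costs 1/40 = 2.5 percentage points. The responder counts below are assumptions for illustration; the intervals are exact 95% CIs.

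| Responders/40 | ORR | 95% CI |
|---|---|---|
| 8 (none lost) | 20.0% | 9.1 to 35.6 |
| 7 (1 lost) | 17.5% | 7.3 to 32.8 |
| 6 (2 lost) | 15.0% | 5.7 to 29.8 |
| 5 (3 lost) | 12.5% | 4.2 to 26.8 |

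More generally, the share of CT responders lost is r × q × s. Here r is the share assessed by PET at Week 16, q the share of those who are PET-negative with a residual mass in a gap cell, and s the share of those whose only qualifying shrinkage is at that visit. None is in the documents. Assume 10 CT responders in 40 (25%), r = 1 and q = 0.2 to 0.4:
- s = 1: 2 to 4 lost, ORR 8/40 = 20% to 6/40 = 15%.
- s = 0.25: 0.5 to 1 lost in expectation, ORR 9.5/40 = 23.75% to 9/40 = 22.5%.
- s = 0, or r = 0: none lost, ORR stays at 25%.

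**The case against.** The strongest reply is that the gap rarely reaches the reported result. BOR takes the best visit, CT is done every 8 weeks, and PET is scheduled only at screening and Week 16, so most responders would qualify on another scan. This stands, and it sets the limit on the point.

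Second, the PR list may not be meant as strictly cumulative. Its opening line is qualified, and its bone-marrow item can apply only to subjects who otherwise meet CR. That is fair, but it does not close the gap: the PET item states its own conditions, and within them a negative PET does not satisfy it.

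Third, the setting is modest. ORR is descriptive, no formal testing is planned (SAP 3.5), Group 3 expansion depends on DLTs, SAP 1.2 does not describe Group 3, and SAP 1.3 reports 33 subjects enrolled in the whole study. Because SAP 6.1.1.2 does not mention the Appendix 5 modifications, it is not certain that the PET item would drive the reported ORR. All this lowers the impact; the uncertainty over which rule governs is itself a reason to settle the text.

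Four stronger readings are tempting but not supported:
- *The subject becomes SD.* The SD wording turns on insufficient shrinkage, which this subject does not have. SD is a default someone might apply, not what the text assigns.
- *Every PET-negative residual mass is lost.* Three of the six combinations remain PR.
- *ORR drops from 25% to 15–20%.* That needs assumed values for r and q, an assumed 10 responders, and every affected response to rest on Week 16 alone (s = 1). It is the upper end for those inputs.
- *ORR is lower at sites with PET, or a negative Week 16 PET also cancels a Week 24 response.* The documents give no site-level PET availability and no rule carrying a PET forward to later visits.

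**Conclusion.** The concern holds at the level of the visit. With a positive baseline PET in either avidity class, or no baseline PET in typically avid disease, adequate shrinkage with a residual mass and a negative PET fits neither CR nor PR, and read literally fits neither SD nor NE. Whichever label is then used, the visit is a non-response, because ORR counts only CR and PR.

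At the level of ORR, the effect is possible rather than automatic, and is downward. It reaches only subjects whose qualifying shrinkage is seen solely at a visit with a negative PET, which on the planned schedule is Week 16. Appendix 5 covers all lymphoma subjects and considers any available PET, so an unscheduled scan could have the same effect. The cost is 2.5 points per affected subject at 40 subjects; the number affected cannot be derived from the documents. This assumes that each visit is classified on its own scans and that the PET item is applied as written. The primary endpoint is untouched. It is a specific classification error worth correcting, with limited consequence for the study's main conclusions.

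**What to change.** Amend the Appendix 5 PR list so that a positive on-treatment PET is not a condition of PR. Suggested rule: a subject who meets the CT criteria for PR and has a negative on-treatment PET is classified as at least PR; a positive PET in a previously involved site precludes CR but does not preclude PR. State explicitly whether a PET-negative residual mass may be upgraded to CR. ORR is the same either way, but the BOR table is not.

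Have SAP 6.1.1.2 name Appendix 5, with this rule, as the lymphoma response definition used to derive BOR.

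The cost is a wording change in the appendix and one line in the SAP. No new scans or data are needed.
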